1.2 Study objectives and endpoints

Objective	Endpoint

Primary
 
The primary objective is to compare the Disease-free survival (DFS) in the canakinumab versus placebo arms as determined by local investigator assessment.
	
DFS determined by local investigator assessment. See Section 2.5.1 for the primary estimand

Key secondary
 
To compare overall survival (OS) in the canakinumab arm versus placebo arm
	
OS. See Section 2.6.1 for the key secondary estimand

Other secondary
 
 1. To compare DFS by local investigator assessment and OS in the canakinumab versus placebo arms in subgroups defined respectively by PD-L1 and CD8 expression levels 2. To compare lung cancer specific survival in the canakinumab arm versus placebo arm 3. To characterize the safety profile of canakinumab 4. To characterize the pharmacokinetics of canakinumab therapy 5. To characterize the prevalence and incidence of immunogenicity (anti-drug antibodies, ADA) of canakinumab 6. To assess the effect of canakinumab versus placebo on PROs (EORTC QLQ-C30 with QLQ-LC13 incorporated and EQ-5D) including functioning and health-related quality of life 	
 1. DFS by local investigator assessment and OS in PD-L1 and CD8 subgroups 2. Lung cancer specific survival (LCSS) 3. Frequency of AEs, ECGs and laboratory abnormalities 4. Serum concentration-time profiles of canakinumab and appropriate individual PK parameters based on population PK model 5. Serum concentrations of anti-canakinumab antibodies 6. Time to 10 point definitive deterioration of symptom scores of pain, cough and dyspnea per QLQ-LC13 questionnaire are primary PRO variables of interest. Time to 10 point definitive deterioration of global health status/QoL, shortness of breath, pain, role functioning, physical functioning and fatigue per QLQ-C30 questionnaire, time to first 10 point deterioration for symptom scores of pain, cough, dyspnea per QLQ-LC13 questionnaire, time to first 10 point deterioration for global health status/QoL, shortness of breath, pain, role functioning, physical functioning and fatigue per QLQ-C30 questionnaire together with the utilities derived from EQ-5D-5L are secondary PRO variables of interest

2 Statistical methods

2.1 Data analysis general information

The futility IA of DFS will be performed by an independent statistician external to Novartis. The final DFS analysis will be the basis of the primary CSR. Novartis will perform the analyses specified in this SAP. SAS version 9.4 or later will be used for analysis.

Data included in the analysis

There is one IA and a final analysis planned for the primary efficacy endpoint of DFS. Up to two IAs and a final analysis may be performed for the key secondary endpoint of OS if DFS is statistically significant. A unique cut-off date will be established after the targeted number of events for the planned interim and final analyses has been documented. For each of the analyses, all statistical analyses will be performed using all data collected in the database up to the data cut-off date. All data with an assessment date or event start date, e.g. vital sign assessment date or start date of an adverse event, prior to or on the cut-off date will be included in the analysis. Any data collected beyond the cut-off date or after subjects withdraw their consent forms will not be included in the analysis and will not be used for any derivations.

All events with start date before or on the cut-off date and end date after the cut-off date will be reported as 'ongoing'. The same rule will be applied to events starting before or on the cut-off date and not having documented end date. This approach applies, in particular, to adverse event and concomitant medication reports. For these cases, the end date will not be imputed and therefore will not appear in the listings.

For any CSR after the primary CSR, a separate set of TFL shells will detail the planned outputs. If futility is claimed at the first DFS IA, neither DFS and OS is statistically significant, or the study is terminated by the sponsor, it can result in an either close-out CSR or abbreviated CSR.

General analysis conventions

Pooling of centers: Unless specified otherwise, data from all study centers will be pooled for the analysis. Due to expected small number of subjects enrolled at centers, no center effect will be assessed.

Qualitative data (e.g., gender, race, etc.) will be summarized by means of contingency tables by treatment arm; a missing category will be included as applicable. Percentages will be calculated using the number of subjects in the relevant population or subgroup as the denominator.

Quantitative data (e.g., age, body weight, etc.) will be summarized by appropriate descriptive statistics (e.g. mean, standard deviation, median, percentiles, minimum, and maximum) by treatment arm.

2.1.1 General definitions

Study treatment

Study treatment will refer to canakinumab or placebo.

Date of first administration of study treatment

The date of first administration of study treatment is defined as the first date when a non-zero dose of canakinumab or placebo is administered and recorded on the Dosage Administration Record (DAR) (e) CRF. The date of first administration of study treatment will also be referred as start of study treatment.

Date of last administration of study treatment

The date of last administration of study treatment is defined as is the last date when a nonzero dose of canakinumab or placebo is administered and recorded on DAR eCRF. The date of last administration of study treatment will also be referred as end of study treatment.

Study day

The study day, describes the day of the event or assessment date, relative to the reference start date.

The study day is defined as:

- the date of the event (visit date, onset date of an event, assessment date etc.) – reference start date + 1 if event is on or after the reference start date;
- the date of the event (visit date, onset date of an event, assessment date etc.) – reference start date if event precedes the reference start date.

The reference start date for safety assessments (e.g. adverse event onset, laboratory abnormality occurrence, vital sign measurement, dose interruption, pk etc.) is the start of study treatment.

The reference start date for all other, non-safety assessments (i.e., disease recurrence, survival, LCSS, ECOG performance status, and patient reported outcomes (PRO)) is the date of randomization.

The study day will be displayed in the data listings. If an event starts before the reference start date, the study day displayed on the listing will be negative.

Time unit

A year length is defined as 365.25 days. A month length is 30.4375 days (365.25/12). If duration is reported in months, duration in days will be divided by 30.4375. If duration is reported in years, duration in days will be divided by 365.25.

Baseline

For efficacy evaluations, the last non-missing assessment, including unscheduled assessments on or before the date of randomization is taken as “baseline” value or “baseline” assessment. In the context of baseline definition, the efficacy evaluations also include PRO and performance status.

For safety evaluations, the last available assessment on or before the date of start of study treatment is taken or “baseline” assessment.

If subjects have no value as defined above, the baseline result will be missing.

On-treatment assessment/event and observation periods

For adverse event reporting the overall observation period will be divided into three mutually exclusive segments:

- **pre-treatment period:** from day of subject’s informed consent to the day before first administration of study treatment
- **on-treatment period:** from date of first administration of study treatment to 130 days (approximately five terminal half-lives of canakinumab) after date of last actual administration of any study treatment (including start and stop date)
- **post-treatment period:** starting at day 131 after last administration of study treatment.

Safety summaries (tables, figures) include only data from the on-treatment period with the exception of baseline data which will also be summarized where appropriate (e.g. change from baseline summaries). In addition, a separate summary for death including on treatment and post treatment deaths will be provided. In particular, summary tables for adverse events (AEs) will summarize only on-treatment events, with a start date during the on-treatment period (**treatment-emergent** AEs).

However, all safety data (including those from the post-treatment period) will be listed and those collected during the pre-treatment and post-treatment period will be flagged.

Windows for multiple assessments

Time windows will be defined for descriptive summary of PRO and ECOG performance status data by visit and longitudinal data analysis (Table 2-1). If more than one assessment is available in the same time window, the assessment closest to the planned date will be considered. If two assessments are obtained with the same time difference compared to the scheduled visit day, the assessment obtained prior to visit will be considered. Data obtained at the end of treatment will be classified as other assessment in the corresponding time window.

Table 2-1 Time windows for PRO and ECOG PS assessments

Time Window	Planned Visit Timing	Time Window Definition
Treatment phase		
Baseline	On or before Study Day 1[a]	≤ Study Day 1
Week 3	Study Day 22	Study Days 2 to 32
Week 6	Study Day 43	Study Days 33 to 53
.....
Week k (with k = 9, 12...)	Study Day 21*(k/3)+1	Study Day 21*(k/3)-9 to 21*(k/3)+11 If last dose date is in the window, upper bound of this time window will be EOT visit date +7

“Note: EOT will be included if EOT is performed within 7 days of permanent discontinuation of study treatment”

Safety follow-up phase

Safety follow-up 1	26 days after treatment discontinuation	[EOT visit date+8; EOT date +39]
Safety follow-up 2	52 days after treatment discontinuation	[EOT visit date+40; EOT date +65]
Safety follow-up 3	78 days after treatment discontinuation	[EOT visit date+66; EOT date +91]
Safety follow-up 4	104 days after treatment discontinuation	[EOT visit date+92; EOT date +117]
Safety follow-up 5	130 days after treatment discontinuation	[EOT visit date+118; EOT date +143]

Post treatment efficacy follow-up phase

Post treatment follow-up (Efficacy follow up)	Every 26 weeks in Year 2 and 3; Every 52 weeks in Year 4 and 5	First time window: [upper bound of the last previous time windows with assessment + 1; TA date + TA interval at next visit/2] Otherwise : [TA date - TA interval at this visit/2; TA date+TA interval at next visit/2]
7 days post disease progression (PRO only)	Within 7 days post disease progression	[disease progression date+1; disease progression date +21]
28 days post disease progression (PRO only)	28 days post disease progression	[disease progression date+22; disease progression date +42]

[a] Study Day 1 = randomization date and PRO assessment on Cycle 1 Day1 will be baseline for PRO if randomization date is not Cycle 1 Day1.

Last contact date

The last contact date will be derived for subjects not known to have died at the analysis cut-off using the last complete date among the following (Table 2-2):

Table 2-1 Last contact date data sources

Source data	Conditions
Date of Randomization	No condition

Source data	Conditions
Last contact date/last date subject was known to be alive from Survival Follow-up page	Subject status is reported to be alive, lost to follow-up or unknown.
Start/End dates from further antineoplastic therapy	Non-missing medication/procedure term.
Start/End dates from drug administration record	Non-missing dose. Doses of 0 are allowed.
Date of disease recurrence	No condition
Laboratory/PK collection dates	Sample collection marked as 'done'.
Vital signs date	At least one non-missing parameter value
Performance Status date	Non-missing performance status
Start/End dates of AE	Non-missing verbatim term

The last contact date is defined as the latest complete date from the above list on or before the data cut-off date. The cut-off date will not be used for last contact date, unless the subject was seen or contacted on that date. No date post cut-off date will be used. Completely imputed dates (e.g. the analysis cut-off date programmatically imputed to replace the missing end date of a dose administration record) will not be used to derive the last contact date. Partial date imputation is allowed for event (death)/censoring is coming from 'Survival information' eCRF.

The last contact date will be used for censoring of subjects in the analysis of overall survival.

2.2 Analysis sets

Full Analysis Set

The Full Analysis Set (FAS) comprises of all subjects to whom study treatment has been assigned by randomization.

According to the intent to treat principle, subjects will be analyzed according to the treatment and strata (AJCC/UICC v8 stage: IIA versus IIB versus IIIA versus IIIB with T>5cm N2 disease; Histology: squamous versus non-squamous; and Region: Western Europe and North America vs. eastern Asia vs. Rest of the world (RoW)) to which they have been assigned during the randomization procedure.

Safety

The Safety Set includes all subjects who received at least one dose of study treatment. Subjects will be analyzed according to the study treatment they received, either canakinumab or placebo. The treatment received is defined as the randomized treatment if the subject took at least one dose of that treatment or the first treatment received if the randomized treatment was never received.

Pharmacokinetic analysis set (PAS)

The Pharmacokinetic analysis set (PAS) includes all subjects who receive at least one dose of canakinumab and provide at least one evaluable PK sample. A PK sample for canakinumab is considered evaluable when subjects have:

- at least one dose of canakinumab prior to sampling, except C1D1 pre-dose sample
- Pre-dose samples collected before the next dose administration
- Pre-dose samples (except for Cycle 1 Day 1) collected between 16 days (384 hours) and 26 days (624 hours) after the last 200 mg canakinumab dose administration
- Received 200 mg of canakinumab prior to post-dose PK sampling

Subject Classification:

Subjects may be excluded from the analysis populations defined above based on the protocol deviations entered in the database and/or on specific subject classification rules defined in [Table 2-3](#).

Table 2-2 Subject classification based on protocol deviations and non-PD criteria

Analysis set	Protocol deviations leading to exclusion	Non protocol deviation leading to exclusion
FAS	No written inform consent	Not applicable
Safety set	No written inform consent	No dose of study medication
PAS	No written inform consent	See definition of PAS

Withdrawal of Informed Consent

Any data collected in the clinical database after a subject withdraws informed consent from all further participation in the trial, will not be included in the analyses. The date on which a subject withdraws full consent is recorded in the eCRF.

Death events may be used in the analysis if captured from public records, local law, and subject informed consent permitting.

Additional data for which there is a separate informed consent, e.g. PK, [REDACTED] etc., collected in the clinical database without having obtained that consent, will not be included in the analyses. These data will be excluded by the presence of the appropriate protocol deviation criterion.

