7.1.5 Withdrawal of consent

Subjects may voluntarily withdraw consent to participate in the study for any reason at any time. Withdrawal of consent occurs only when a subject:

- Does not want to participate in the study anymore, and
- Does not allow further collection of personal data

In this situation, the investigator should make a reasonable effort (e.g. telephone, e-mail, letter) to understand the primary reason for the subject's decision to withdraw his/her consent and record this information. Where consent to the use of Personal and Coded Data is not required in a certain country's legal framework, the subject therefore cannot withdraw consent. However, they still retain the right to object to the further collection or use of their Personal Data.

Study treatment must be discontinued and no further assessments conducted, and the data that would have been collected at subsequent visits will be considered missing.

Further attempts to contact the subject are not allowed unless safety findings require communicating or follow-up.

All efforts should be made to complete the assessments prior to study withdrawal. A final evaluation at the time of the subject's study withdrawal should be made as detailed in the assessment table.

Novartis will continue to keep and use collected study informational research research results (data) that have already been collected for the study evaluation, (including processing of biological samples that has already started at time of consent any data resulting from the analysis of a subject's samples until their time of withdrawal/opposition.) according to applicable law. No new Personal Data (including biological samples) will be collected following withdrawal of consent/opposition.

For US and Japan: All biological samples not yet analyzed at the time of withdrawal may still be used for further testing/analysis in accordance with the terms of this protocol and of the informed consent form.

For EU and RoW: All biological samples not yet analyzed at the time of withdrawal will no longer be used, unless permitted by applicable law. They will be stored according to applicable legal requirements.

Applicable for sub-study:

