7.1.6.2 Survival

All subjects who discontinue from the study treatment will be followed up every 12 weeks for survival until the final overall survival (OS) analysis or death, lost to follow-up or withdrawal of consent for survival follow-up (see Table 7-1). Additional survival assessments may be performed outside the 12 weeks follow-up schedules if a survival update is required for an interim assessment to meet safety or regulatory needs. The investigator or his designee will collect this survival information and any new anti-neoplastic therapies for all subjects until the final survival analysis. Follow-up can be done via a phone contact.

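### For OS, public-record deaths after consent withdrawal may count but no matching alive date is provided, so censoring depends on outcome, and SAP 2.1 and 2.2 need one rule

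*SAP*

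**What the plan says.** - **SAP 2.1 (data included):** information dated "after subjects withdraw their consent forms will not be included in the analysis and will not be used for any derivations". No exception is given.
- **SAP 2.2 (withdrawal of informed consent):** the general bar is repeated for data collected "after a subject withdraws informed consent from all further participation in the trial, will not be included in the analyses". An exception for deaths only follows: "Death events may be used in the analysis if captured from public records, local law, and subject informed consent permitting".
- **SAP 2.1.1 (last contact date):** "The last contact date will be used for censoring of subjects in the analysis of overall survival". The listed sources are trial records such as the survival follow-up page, dosing, laboratory, vital signs and AE dates. A public-record search is not among them.
- **Protocol 7.1.5:** a subject who withdraws consent is one who does not allow further collection of personal data. "No new Personal Data (including biological samples) will be collected following withdrawal of consent/opposition", and "the data that would have been collected at subsequent visits will be considered missing".
- **Protocol 7.1.6.2:** survival follow-up runs to final OS analysis, death, "lost to follow-up or withdrawal of consent for survival follow-up".
- **SAP 2.5.3:** a subject without a DFS event is censored at the last adequate tumor assessment. Consent withdrawal is a listed censoring reason. A death after withdrawal is not addressed.

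**The concern.** The exception works in one direction only. Take two subjects who withdraw at month 6 in a country where death records may be searched. One dies at month 30 and can be counted as an event at month 30. The other is alive at month 30 but is censored no later than month 6, because no source supplies a later alive date and SAP 2.1 keeps post-withdrawal dates out of any derivation. The second subject's 24 months at risk are dropped because that subject survived. Kaplan-Meier and Cox estimates assume that censoring carries no information about later outcome, and here it does.

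The SAP does not also say whether the exception is to be used: it says deaths may be used, without naming the endpoint, and SAP 2.1 would exclude them. Two programmers could build different OS datasets from the same plan. At stake are the OS curves and event rates and, if withdrawal or record capture differs by arm, the OS hazard ratio.

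**Working it through.** **Inputs from protocol 10.8 and 10.9.** Placebo median OS 66 months; OS hazard ratio 0.776; 1500 subjects randomized 1:1 over 30 months; final OS analysis at 63 months; OS loss 3% per year, not split by cause.

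**Assumed, not in the documents.** Exponential survival, withdrawal of 1–3% per year, and 50–100% of post-withdrawal deaths found. Withdrawal is taken as non-informative at first.

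**Plan's own figures first.** With these inputs, expected deaths are 318, 414 and 507 at 42, 52 and 63 months (plan: 318, 418, 504). Cumulative power with a three-look Lan-DeMets O'Brien-Fleming boundary is 37.1%, 64.5% and 80.2% (plan: 36.26%, 64.09%, 79.25%). The sample size is not in question.

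**Effect of the rule.** Let *h* be the monthly death hazard, *w* the monthly withdrawal hazard and *f* the months to cut-off. If all deaths are found:

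- deaths per subject: D = 1 − exp(−hf)
- person-months under complete follow-up: D/h
- person-months dropped from withdrawn survivors: exp(−hf) × [f − (1 − exp(−wf))/w]
- observed rate: D ÷ (D/h − dropped person-months)

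**One case by hand.** Placebo, f = 48 (middle of the 33–63 month range), 3% per year:

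- h = ln 2/66 = 0.010502; w = −ln(0.97)/12 = 0.002538
- exp(−hf) = 0.6040; D = 0.3960; D/h = 37.70
- dropped: 0.6040 × 2.809 = 1.70, leaving 36.01 person-months
- rate: 0.3960/36.01 = 0.0110, which is 1.047 times the true hazard

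At 1% per year, w = 0.0008375, the dropped time is 0.6040 × 0.952 = 0.575, and the ratio is 1.015.

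**Averaged over uniform accrual, cut-off at 63 months:**

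| Withdrawal per year, both arms | Deaths found | Placebo rate | Canakinumab rate | HR (true 0.776) |
|---|---|---|---|---|
| 1% | 50% | +0.8% | +0.8% | 0.776 |
| 1% | 100% | +1.6% | +1.7% | 0.777 |
| 3% | 50% | +2.4% | +2.6% | 0.777 |
| 3% | 100% | +4.7% | +5.1% | 0.778 |

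Simulation with 2 million subjects per arm agrees to within about 0.3 percentage points. Censoring everyone at withdrawal, or using both deaths and alive status to cut-off, returns the true rate.

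**Unequal withdrawal, true HR 1.00.** At 3% per year on canakinumab and 1% on placebo, the rule gives 1.03 with all deaths found and 1.016 with half found. Reversing the arms gives 0.97 and 0.984.

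**Informative withdrawal.** Suppose the death hazard rises after withdrawal (multipliers assumed; placebo, 3% per year). Error in the rate against complete follow-up:

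| Hazard multiplier | Censor all at withdrawal | SAP 2.2 exception, 50% to 100% found |
|---|---|---|
| 1.5 | −2.5% | +0.8% to +4.0% |
| 2 | −4.5% | −0.5% to +3.3% |
| 3 | −7.5% | −2.5% to +2.4% |

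Censoring at withdrawal is therefore not a safe default. Only two-sided ascertainment avoids the error in both settings.

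**DFS at 42 months.** Further assumptions: 10–20% of DFS events are deaths without recurrence, median survival after recurrence is 15–20 months, and all deaths are found. Counting post-withdrawal deaths raises the DFS rate by about 0.3–0.5% at 1% withdrawal per year and about 2% at 5% per year, the plan's full DFS dropout rate. That is 2 to 10 extra events on roughly 395–415.

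**The case against.** **The SAP is not really inconsistent.** The exception in SAP 2.2 directly follows the general bar there, and a specific provision can be read as qualifying the general one in SAP 2.1. That is a fair reading and makes the conflict partly editorial. It does not supply the missing alive date.

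**The exception limits itself.** It applies only where local law and the subject's consent permit. A reader might infer that SAP 2.2 flatly contradicts protocol 7.1.5. The documents do not support that. Protocol 7.1.5 also recognizes countries where consent to data use is not required, and protocol 7.1.6.2 refers to a separate withdrawal from survival follow-up. The passages are in tension: given how protocol 7.1.5 defines withdrawal, the consent condition would seldom be met.

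**DFS.** A reader might infer that DFS is inflated by the same discarding of alive evidence. It is not. SAP 2.5.3 censors every subject without a DFS event at the last adequate tumor assessment, so proof of being alive never extends DFS follow-up. In addition, the third sensitivity analysis in SAP 2.5.4.1 censors subjects with two or more missing assessments. What remains is a small effect and an unstated rule.

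**The size is an upper range.** Treating the whole 3% yearly loss as withdrawal, with 50–100% of deaths found, is generous given the law-and-consent condition. This stands.

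**OS is no longer tested.** The close-out SAP reports that the primary endpoint was not met, so no type I error is at stake. It still plans OS summaries overall and by PD-L1 and CD8, with Kaplan-Meier and forest plots, and those are what the rule would distort.

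**Conclusion.** The point holds for OS. As written, the exception makes censoring depend on later survival, and SAP 2.1 and 2.2 cannot both be followed literally. The SAP nowhere says that alive evidence is to be discarded; this follows from SAP 2.1, 2.1.1 and 2.2 read together.

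With non-informative withdrawal, the OS event rate is overstated by about 0.8–1.6% at 1% withdrawal per year and about 2.4–5% if all planned OS loss is withdrawal. A reader might infer that the OS treatment comparison is compromised. With equal withdrawal it is not: the hazard ratio changes by less than 0.003. It shifts by about 3% only with a difference such as 3% v 1% per year and every death found, and nothing in the documents shows that withdrawal differed by arm.

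Withdrawal rates, record capture and post-withdrawal hazards are all assumptions. The issue deserves correction because the repair is cheap and OS is still reported descriptively.

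**What to change.** 1. **OS, SAP 2.2.** Where law and consent permit a public-record search, apply it to all withdrawn subjects in both arms. Count the deaths found. For those not found dead, take the search date, or the cut-off if earlier, as last known alive. Add this source to the last-contact table in SAP 2.1.1.
2. **No search permitted.** Censor at the last contact on or before withdrawal.
3. **Sensitivity analysis.** Report OS with all withdrawn subjects censored at withdrawal, noting that this is unbiased only if withdrawal is non-informative.
4. **Consistency.** Have SAP 2.1 cross-refer to the exception, and reconcile it with protocol 7.1.5 by stating when consent is taken to permit a search.
5. **DFS.** State in SAP 2.5.3 whether deaths after withdrawal count.

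The cost is a few sentences, one added date source, one programming rule, one extra OS table and the record search itself where it is allowed. A subject not found in incomplete records may be wrongly taken as alive, so the completeness of each source should be described.
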